Effect of Caloric Restriction and Protein Intake on Metabolism and Anabolic Sensitivity

NCT02945410

10 May 2019

1. What is the significance/purpose of the project?

Successful weight loss requires the induction of an energy deficit [1], which can be attained through caloric restriction, exercise, or a combination of both [2]. However, weight loss is not only associated with the favorable loss of adipose tissue, but also with the loss of lean mass [2]. On average, approximately 25% of weight loss consist of lean mass [3], but lean mass loss is even more pronounced in normal-weight individuals [4]. The loss of lean mass during energy deficiency is a result of the degradation of body protein to provide additional energy and substrates to meet the high glucose demand of the brain. Protein degradation takes place primarily in expendable cellular tissues such as the skeletal muscle, which is emphasized by recent findings of reduced muscle protein synthesis [5] and increased muscle protein breakdown [6] during energy deficiency. As a result, energy deficiency and the concomitant loss of lean mass could be associated with undesired health effects such as impaired blood glucose regulation [7] and the loss of functional capacity throughout the life span [8].

Energy deficiency is associated with metabolic and anti-anabolic adaptations. Parallel with the loss of lean mass, resting metabolic rate (RMR) is also suppressed during energy deficiency. Because this reduction in RMR conserves energy, it has been linked to attenuated weight loss and an increased propensity for weight (re)gain [9]. The reduction in RMR is a consequence of the suppression of expendable functions, such as growth and reproduction, in order to conserve energy for life-sustaining functions [10]. As a result, the secretion and bioavailability of anabolic hormones is strongly impaired during energy deficiency [11]. This suppression of anabolic hormones is not only linked to the loss of skeletal muscle, but has also detrimental effects on bone [12-14]. This is particularly concerning because the accrual and maintenance of peak bone mass during adolescence and adulthood is a strong predictor of osteoporosis risk later in life [15].

The profound metabolic consequences of caloric restriction may negate some of the benefits of weight loss. Considering that calorie restriction is the preferred and most-effective strategy for the treatment and prevention of overweight and obesity and their associated comorbidities [2], strategies are needed to preserve the beneficial effects of calorie restriction while attenuating its potentially detrimental effects on metabolism, skeletal muscle, and bone. Lean mass can be preserved through increased dietary protein intake. A high dietary protein intake during energy deficiency attenuates the loss of lean mass and improves protein balance [16, 17].

Further, it is known that a high protein intake, particularly when coupled with exercise, is associated with improved bone strength [18], and effect that is likely modulated by the stimulating effects of dietary protein on the secretion of IGF-1 [15]. These findings lend to the idea that increased protein intake during calorie restriction may preserve the anabolic sensitivity of both skeletal muscle and bone.

However, only little is known about the underlying mechanisms, particularly pertaining to the effects of an increased protein during caloric restriction on circulating concentrations of anabolic hormones and the downstream effects on bone turnover. Therefore, the purpose of our study is to determine whether a strategy of increased dietary protein during energy deficiency can attenuate the suppression of RMR and reductions in hormones with anabolic and anti-catabolic effects on bone. For this purpose, we will conduct a prospective, randomized controlled study involving three experimental conditions: a) calorie restriction with normal protein intake (0.8 g/kg; CR-NP); b) calorie restriction with high protein intake (1.7 g/kg; CR-HP); and c) a control period of balanced caloric intake and matched protein intake (1.7 g/kg; CON).

Aim 1: To determine whether increased protein intake can preserve metabolic function and maintain anabolic sensitivity during calorie restriction

Hypothesis 1A: Weight loss will be similar following CR-HP and CR-LP, but the loss of lean mass and the suppression of resting metabolic rate will be reduced in CR-HP when compared to CR-NP.

Hypothesis 1B: The reduction in circulating concentrations of the anabolic hormones IGF-1, insulin, and testosterone will be attenuated in CR-HP when compared to CR-NP.

Informed Consent: The researcher (or designee) obtaining informed consent will thoroughly review the consent form with each participant and confirm that the participant understands all study procedures and potential risks and benefits of study participation.

Initial Anthropometric Measurements: After obtaining informed consent, participants will be weighed to the nearest 0.1 kg on a digital scale in the laboratory with a standard outfit of t-shirt and gym shorts. Participants also will have their body fat percentage determined using caliperometry. A skinfold caliper will be used to take measurements of skinfold thickness at 7 sites (abdomen, triceps, chest, midaxillary, subscapular, suprailliac, and thigh). The skinfold measurements will be used to calculate body density and body fat percentage (ACSM's Guidelines for Exercise Testing and Prescription, Ninth Edition).

Questionnaires: Participant will then fill out the following questionnaires:

- o The Eating Disorder Inventory a self-report questionnaire used to assess the presence of eating disorders (D. M. Garner & Olmstead, 1991; David M. Garner, Olmstead, & Polivy, 1983).
- o The Health Exercise and Nutrition Questionnaire, which includes questions regarding demographics, medical history, current and past exercise, bone health, stress fracture history, current medication and supplement use, and dietary habits.
- o The Brief Calcium Assessment Tool, a brief questionnaire used to assess habitual dietary calcium intake (Yang, Martin, & Boushey, 2010).
- o The Bone-Specific Physical Activity Questionnaire, a questionnaire used to predict. The BPAQ predicted indices of bone strength at clinically relevant sites in both men and women (Weeks & Beck, 2008)
- o Absolute and Relative Contraindications to Exercise Testing, a questionnaire pertaining to absolute and relative contraindications to exercise testing to determine if the participant is able to exercise adequately (ACSM's Guidelines for Exercise Testing and Prescription, Ninth Edition).

After admittance into the study, participants will be provided with an over-the-counter calcium and vitamin D supplement. Supplementation of calcium and vitamin D will be initiated at least 2 weeks prior to the start of the first intervention to maintain the participants intake at levels required for optimal bone health.

3. Preliminary testing

Prior to study start, body composition will be assessed with a bioimpedance analyser (Bodystat Quadscan 4000). Peak oxygen uptake (VO₂peak) will be assessed using an incremental exercise test on a bicycle ergometer (Monark LC6).

4. Randomization

Each participant will be randomly assigned to one of the six possible permutations of the order of the study conditions (CON/CR-LP/CR-HP). Randomization of study condition order will occur in blocks of 6.

5. Nutritional intervention:

After randomization of study condition order, participants will proceed through each of the following conditions. Each condition will last 5 days with a post-test on day 6:

CR-LP: Participants will consume 30 kcal/kg FFM/day and 0.8 g protein/kg BW/day.

CR-HP: Participants will consume 30 kcal/kg FFM/day and 1.7 g protein/kg BW/day.

CON: Participants will consume 55 kcal/kg FFM/day and 1.7 g protein/kg BW/day.

Dietary energy intake prescriptions will be controlled individually utilizing a combination of two clinical products (Ensure Original and Ensure High Protein, both Therapeutic Nutrition, Abbot) and maltodextrin (Tate & Lyle) such that the target energy intake of 30 kcal/kg FFM/day (CR-LP and CR-HP) or 55 kcal/kg FFM/day (CON) is reached. Participants will be provided clear plastic bottles each day with the prescribed amount of the clinical products and will be asked to consume all of it during the day.

6. Prescribed Exercise

During each conditions, participants will conduct daily supervised exercise on a bicycle ergometer (Monark LC6) at an exercise intensity of 60% VO₂peak. Exercise duration will be adjusted individually such that exercise energy expenditure will amount to 15 kcal/kg FFM/day. Exercise will take approximately 60-90 minutes. Additional exercise and intense physical activity will be prohibited. Compliance will be monitored using an activity monitor (Actigraph). Activity monitors will be returned at the end of each study period.

7. Washout

Once a participant completes a study condition, they will be allowed a washout period before beginning the next study condition. Washout periods between conditions will be 14 days to allow protein balance to return to baseline (Hoffer & Forse, 1990). During this time, participants will resume their regular diet and physical activity. Calcium and vitamin D supplementation will continue to maintain their intake at levels required for optimal bone health.

8. Assessments

All assessments will be identical during each study condition, which lasts for 5 days and includes post testing on day 6. On day 1 and 6, participants will arrive at the lab in the morning following an overnight fast and undergo the following assessments:

- o Bioimpedance: Body composition is assessed with a bioimpedance analyser (Bodystat Quadscale 4000). While lying in the supine position (with no parts of the body touching one another), four electrodes are attached to the wrist, hand, ankle and foot on the right side of the body. The cables from the bioimpedance analyzer are then attached to the electrodes and the device is turned on, running an electrical current through the body to estimate body composition.
- o Resting Metabolic Rate: Resting Metabolic Rate (RMR) will be measured following an overnight fast (no food or drink, except water, 12 hours before the scheduled test) between 6-10:00 a.m. and before exercise. Participants will be asked to lie supine at rest for 30 minutes in order to achieve a steady state prior to measurement. Oxygen consumption and carbon dioxide production will then be measured with a ventilated hood system (COSMED Quark CPET Metabolic Testing System) for 30-45 minutes. For the determination of RMR, only data during steady state will be used, which is defined as variations in oxygen uptake, carbon dioxide production of less than 10%, and in respiratory quotient by less than 5% for at least 10 minutes. RMR will be calculated from oxygen uptake and carbon dioxide production using the Weir equation (Weir, 1949).
- o Fasting Blood Collection: A fasting blood sample will be collected from a forearm vein by trained personnel.
- o VO₂peak: Participants will be asked to complete a graded cycle ergometer test to determine aerobic fitness (VO₂ peak). Participants will begin cycling on the bicycle ergometer at 60 W for 3 minutes. The work rate will be increased by 35 W every 3 minutes until exhaustion (Achten & Jeukendrup, 2003). Exhaustion is operationally defined when at least two of the following are met: 1) 90% age predicted heart rate max [220-age], 2) respiratory exchange ratio 1.1, 3) a rate of perceived exertion 19, 4) a plateau in VO₂ despite an increase in workload, 5) and/or unable to maintain a pedal rate of 60 rpm. During the test, expired gases will be measured through indirect calorimetry (COSMED Quark CPET Metabolic Testing System), and heart rate will be monitored through telemetry (Garmin).
- o Questionnaires: The Three-Factor Eating Questionnaire, a questionnaire that measures three dimensions of human eating behavior (cognitive dietary restraint, disinhibition, hunger) (Stunkard & Messick, 1985), The Profile of Mood States (POMS), a questionnaire used to assess overall mood. This

profile describes six sub-components of the overall mood construct: anger, confusion, depression, fatigue, tension and vigor (McNair et al., 1971); an abbreviated version of the Eating Disorder Inventory, a self-report questionnaire used to assess the presence of eating disorders (D. M. Garner & Olmstead, 1991; David M. Garner, Olmstead, & Polivy, 1983); Satiety/Hunger Questionnaire: Participants will complete a visual analog scale (VAS) which quantifies 1) appetite, 2) fullness, 3) perception of quantity of food which can be eaten, 4) nausea, 5) thirst, and 6) stress

3. Describe how long, in terms of time, the procedures will take the participant to complete. The description should include the duration of a session, the number of sessions, over what period of time and the total time required to complete the procedures.

Following screening, the study will take at least 9 weeks to complete:

- 2 week pre-study period for preliminary testing and calcium/vitamin D equilibration
- 6 days per study condition (3x)
- Minimum 2 weeks between study conditions (2x)

4. Statistical Analysis Plan

Paired one-sided t tests will be used to assess whether changes from baseline are significantly different from 0. Where significant differences from 0 exist and differences between groups would be expected, additional t tests will be used to compare change scores between CR-LP and CR-HP or CR-HP and CON. Differences between CR-LP and CON will not be evaluated due to the existence of two manipulated variables (protein and kcal) causing the difference in those groups. If exploratory analyses are conducted, multiple comparisons will be corrected for using Holm's sequential version of the Bonferroni correction (Holm S 1979).

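### Nothing in the plan masks CR-HP against CR-LP: the two isocaloric liquid diets go out in clear bottles with no coding or matching described, and the choice of RMR segment is left open

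*Combined protocol and SAP*

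**What the plan says.** All references are to the combined protocol and SAP.

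- **Section 2, item 5 (Nutritional intervention)** sets the targets. For the lower-protein restriction diet it reads: "CR-LP: Participants will consume 30 kcal/kg FFM/day and 0.8 g protein/kg BW/day". The higher-protein restriction diet keeps that energy target and raises protein to 1.7 g/kg; the control diet pairs the same raised protein with 55 kcal/kg FFM. All three diets are made up from a "combination of two clinical products (Ensure Original and Ensure High Protein, both Therapeutic Nutrition, Abbot) and maltodextrin (Tate & Lyle"). On how they are handed out: "Participants will be provided clear plastic bottles each day with the prescribed amount of the clinical products". The recipe for each condition, the drink volumes, any labels and the person who prepares the bottles are not given.
- **Section 2, item 4 (Randomization)** assigns the order of conditions in blocks of six. It says nothing about concealment or masking, and neither does any other section.
- **Section 1** frames Hypotheses 1A and 1B, and the bone-resorption part of 2A, as CR-HP against the lower-protein restriction diet (called CR-NP there, CR-LP in most other places). **Section 4 (Statistical Analysis Plan)** makes this one of two between-condition comparisons of change scores.
- **Section 2, item 8 (Assessments)** records RMR for 30-45 minutes. "For the determination of RMR, only data during steady state will be used", which means at least 10 minutes with less than 10% variation in oxygen uptake and carbon dioxide production and less than 5% in respiratory quotient. For VO₂peak, "The work rate will be increased by 35 W every 3 minutes until exhaustion". Among the questionnaires, "Participants will complete a visual analog scale (VAS) which quantifies 1) appetite, 2) fullness"; mood and eating-behaviour scales are also self-reported.

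**The concern.** With CON, energy intake differs so much that masking would be hard. CR-LP and CR-HP share an energy target, a liquid form and a set of ingredients, so this is the one comparison where masking is plausible, and it is also the one that matters most. A clear bottle hides neither volume nor appearance, and no other safeguard is described. In a crossover every participant meets both drinks, for five days each, and can compare them directly.

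If the condition becomes known, the hypotheses point in a stated direction, and expectation can act wherever there is judgement or effort. Those places are the choice of RMR segment, encouragement and effort in the exercise test, questionnaire answers, and eating away from the laboratory.

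**Working it through.** The plan gives no sample size, effect size, standard deviation or product composition, so there is no planned figure to reproduce. The check has three parts.

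**1. Must the two recipes differ?**
Inputs from item 5: 30 kcal/kg FFM/day for both diets; protein 0.8 and 1.7 g/kg BW/day. Assumptions: 4 kcal per g protein; body fat 10-30%, so FFM is 0.90-0.70 of body weight.
- Protein ratio: 1.7 / 0.8 = 2.125.
- Energy per kg body weight: 30 × 0.90 = 27 kcal, down to 30 × 0.70 = 21 kcal.
- Protein share of energy, CR-LP: 0.8 × 4 / 27 = 11.9%, up to 3.2 / 21 = 15.2%.
- Protein share of energy, CR-HP: 1.7 × 4 / 27 = 25.2%, up to 6.8 / 21 = 32.4%.
- Energy exchanged between protein and other sources: 0.9 × 4 / 27 = 13.3%, up to 3.6 / 21 = 17.1%.

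So the mixtures must differ. Whether the difference can be seen is a separate question.

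**2. Must the volumes differ?**
Take a 75 kg participant with 15% body fat (assumed). Energy is 30 × 75 × 0.85 = 1,912.5 kcal/day; protein is 0.8 × 75 = 60 g or 1.7 × 75 = 127.5 g. Product compositions are all assumed: product A 0.8-1.2 kcal/ml and 0.03-0.05 g protein/ml; product B 0.5-0.9 kcal/ml and 0.06-0.08 g/ml. CR-LP is taken as A plus maltodextrin, and CR-HP as A plus B or as B plus maltodextrin. Volumes count the liquid products only.
- Low end: CR-HP 127.5 / 0.08 = 1,594 ml; CR-LP 60 / 0.03 = 2,000 ml; ratio 0.80.
- High end: CR-HP from 2,217 ml of A (0.8 kcal/ml, 0.05 g/ml) and 277 ml of B (0.5 kcal/ml, 0.06 g/ml), about 2,495 ml in all; CR-LP 60 / 0.05 = 1,200 ml; ratio 2.08.
- Near-equal case: CR-LP at 35 g/L is 60 / 35 = 1.71 L; CR-HP at 70 g/L is 127.5 / 70 = 1.82 L, a gap of about 6%.

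The drinks could match closely or differ plainly. The documents do not settle it, and they describe nothing that would make the volumes match.

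**3. Where could knowledge of the condition enter a hypothesis outcome?**
A 30-minute recording holds 30 / 10 = 3 non-overlapping 10-minute segments, and a 45-minute one holds 4. Each has to pass the criteria, but the plan does not say whether the earliest, the steadiest, the lowest or the mean of all qualifying segments is used.

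Write b for the average shift that segment choice adds to one reading. The CR-HP minus CR-LP contrast of day 6 minus day 1 changes then moves by (b_HP,6 − b_HP,1) − (b_LP,6 − b_LP,1). If the choice ignores condition, this is zero on average and only noise is added. If it follows condition, the shift goes straight into the tested difference. The plan gives no value for b.

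The other outcomes set side by side:

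| Outcome | In Hypotheses 1A, 1B or 2A? | Exposure to expectation |
|---|---|---|
| RMR | Yes | Segment choice open |
| Weight, lean mass (bioimpedance) | Yes | Instrument reading, lower |
| IGF-1, insulin, testosterone, bone markers | Yes | Laboratory reading, lower |
| VO₂peak | No | Effort-dependent |
| Appetite VAS, mood and eating scales | No | Self-reported |

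**The case against.** The strongest reply is that the plan is silent on masking, and silence is not proof of unmasking. A clear bottle is not a labelled one, and decanting may even remove the branding. Three stronger readings are tempting, and the documents support none of them.

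- **A reader might infer that participants and staff can tell the diets apart.** The plan does not say which diet takes more product or more maltodextrin, that the drinks differ in look or taste, or that the people who handle bottles also read RMR. The near-equal volumes above show that a visible difference is not guaranteed.
- **A reader might put a size on the RMR bias**, for example 2-5% of 1,700 kcal/day, which is 34-85 kcal/day. Both inputs are assumptions. The 10% limit governs variation within a steady-state period, not the gap between two qualifying periods. No expected effect is stated against which to judge the result.
- **A reader might call full masking nearly free.** Staffing is not described, so separating preparers from testers cannot be costed from the documents.

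It also stands that most hypothesis outcomes are laboratory or instrument readings, that the RMR criteria are numeric, and that exhaustion in the exercise test has stated criteria. Supervised exercise, the ban on extra exercise and activity monitoring cover part of the behavioural route. Eating outside the protocol stays open, and opaque bottles would not prevent it.

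None of this answers the core point. The one packaging choice that the plan does state offers no concealment, and the RMR selection step has no tie-break.

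**Conclusion.** The concern holds in a limited form. For the main hypothesis contrast, no masking, coding or matching is described, and RMR is the hypothesis outcome where that leaves room for discretion. VO₂peak and the questionnaires are more open to effort or self-report, but no hypothesis depends on them.

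The size of any bias cannot be derived. What follows from the targets is that protein differs 2.125-fold at equal energy, so the mixtures differ. The volume ratio of about 0.8 to 2.1 rests wholly on assumed compositions and one assumed participant. This is a worthwhile, inexpensive improvement to the design; it does not show that the results would be biased.

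**What to change.** 1. In Section 2, item 5, replace the clear bottles with opaque, coded ones, and bring CR-LP and CR-HP to the same total volume for each participant. The energy and protein targets do not change.
2. In Section 2, item 8, fix the RMR rule in advance, for example the first qualifying 10-minute segment, and apply it to files coded for condition.
3. Run the assays, and the CR-LP against CR-HP analysis in Section 4, on coded samples and data.
4. State who is masked for CR-LP against CR-HP, and that CON is not masked.

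The cost is opaque bottles, water and a code list, with no added visit or procedure. Taste or texture may leave participant masking partial. Items 2 and 3 still protect the reading and analysis of outcomes if it does. Full separation of those who prepare the bottles from those who test should be done only where existing staffing allows.

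### A day-1 to day-6 change tested against 0 cannot be attributed to calorie restriction alone, and the controlled comparison with CON is conditional for CR-HP and excluded for CR-LP

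*Combined protocol and SAP*

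**What the plan says.** Section 4 (Statistical Analysis Plan) sets out a sequence.

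- First step, for each condition: "Paired one-sided t tests will be used to assess whether changes from baseline are significantly different from 0". Section 2, item 8 (Assessments) places the measurements on days 1 and 6 of each condition.
- Second step, conditional on the first: "Where significant differences from 0 exist and differences between groups would be expected", then "additional t tests will be used to compare change scores between CR-LP and CR-HP or CR-HP and CON".
- One comparison is ruled out: "Differences between CR-LP and CON will not be evaluated due to the existence of two manipulated variables", these being protein and energy.

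Section 2, item 6 (Prescribed Exercise) applies to all conditions: "During each conditions, participants will conduct daily supervised exercise on a bicycle ergometer", with duration set so that "exercise energy expenditure will amount to 15 kcal/kg FFM/day". Item 5 (Nutritional intervention) builds the intake in all three conditions from two bottled clinical products and maltodextrin. Item 7 (Washout) returns participants to their usual diet and activity between conditions.

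Section 1 describes CON as "a control period of balanced caloric intake and matched protein intake (1.7 g/kg; CON"). Hypotheses 1A, 1B and the resorption half of 2A compare the two restricted conditions with each other. The formation half of 2A refers both of them to CON. Section 1 mostly calls the normal-protein restricted condition CR-NP, while sections 2 and 4 call it CR-LP; CR-LP is used below.

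**The concern.** A test against 0 takes no movement between day 1 and day 6 as the no-effect state. That would be a suitable reference for calorie restriction only if nothing else changed over those days. Here the cycling, the formula diet, any change in protein from the usual diet, and time itself all fall within the same interval, in CON as well as in the restricted conditions. RMR, insulin, other hormones and bone markers could move for those reasons. The randomised reference for the shared part is the same participant's change under CON.

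Both aims presuppose that restriction suppresses or raises something, and then ask whether protein attenuates it. If the presupposed effect is read off the before-after test, a shared shift can create it, or can mask it when it runs the other way. Nothing in section 4 marks the tests against 0 as descriptive.

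**Working it through.** The documents give no sample size, SD, effect size or alpha, so there is no planned figure to reproduce. The check is first one of design, then an illustration under stated assumptions.

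**What each test isolates** (prescriptions from section 2, items 5 and 6)

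| Condition | Intake, kcal/kg FFM/day | Exercise, kcal/kg FFM/day | Intake minus exercise | Protein, g/kg/day |
|---|---|---|---|---|
| CON | 55 | 15 | 55 − 15 = 40 | 1.7 |
| CR-HP | 30 | 15 | 30 − 15 = 15 | 1.7 |
| CR-LP | 30 | 15 | 30 − 15 = 15 | 0.8 |

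Write the mean change as s in CON, s + r in CR-HP and s + r + p in CR-LP. Here s is the shift from exercise, formula diet and time (with protein at 1.7 g/kg), r is the effect of restriction, and p is the effect of the lower protein under restriction.

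- Test against 0 in CR-HP: s + r. In CR-LP: s + r + p.
- CR-HP minus CON: r. Planned, but conditional.
- CR-HP minus CR-LP: −p. Planned, but conditional; s cancels.
- CR-LP minus CON: r + p. Excluded by the SAP; s cancels here too.

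**Illustration 1: no restriction effect, shift in the tested direction.** Assumptions, none from the documents: one-sided alpha 0.05 and a shift of d SDs of the change score. The rejection probability of the paired t test is P(T > t(0.95, n−1)), with T non-central t on n−1 df and noncentrality d√n. For n = 12 and d = 0.5 the noncentrality is 0.5 × √12 = 1.73 and the probability is 0.49. At d = 0.3 it is 0.25 for n = 12 and 0.41 for n = 24.

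| n (assumed) | d = 0.2 | d = 0.5 | d = 0.8 |
|---|---|---|---|
| 6 | 0.11 | 0.28 | 0.52 |
| 12 | 0.16 | 0.49 | 0.83 |
| 18 | 0.20 | 0.65 | 0.95 |
| 24 | 0.24 | 0.77 | 0.98 |

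In 40,000 simulated crossover trials per setting (within-person correlation of change scores 0.5), the contrast with CON rejected in 4.7% to 5.2%, whatever the shift.

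**Illustration 2: real restriction effect of 0.8 SD, opposing shared shift of 0.5 SD.** The net change is 0.8 − 0.5 = 0.3 SD. The SAP does not say which condition's change must be significant for the second step; here it is taken to be the restricted condition's.

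| n (assumed) | Test against 0 rejects | Contrast with CON, correlation 0.5 | Contrast with CON, correlation 0 |
|---|---|---|---|
| 6 | 0.157 | 0.518 | 0.328 |
| 12 | 0.252 | 0.829 | 0.576 |
| 18 | 0.336 | 0.946 | 0.745 |
| 24 | 0.414 | 0.984 | 0.852 |

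The SD of the difference between two changes is √(2(1 − correlation)) times the SD of one. That is 1 at correlation 0.5 and 1.414 at correlation 0, so in the last column the effect is 0.8/1.414 = 0.57 SD.

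**The case against.** The strongest reply is that the plan already contains the controlled test. CR-HP and CON differ only in energy, and their change scores are to be compared. A reader might infer from the first step alone that the trial has no controlled test of restriction; that is not so. For CR-HP, a false restriction claim that follows the full sequence must also pass the contrast with CON, so its probability cannot exceed about 5%. In the simulation both tests rejected in 4.4% of trials at n = 12 with a shift of 0.5 SD, against 49% for the first test alone.

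Two further replies have force. A test of change against 0 is a valid test of change, and the SAP sentence does not itself attribute the change to restriction. Most hypotheses compare CR-HP with CR-LP, where a shared shift cancels. A reader might infer that the protein comparison is biased; the documents do not support that either. Finally, habitual exercise is not reported and extra exercise is prohibited during the conditions, so the cycling may partly replace usual training. The size and direction of any shift are unknown.

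These points narrow the concern but do not remove it. The controlled CR-HP contrast is carried out only where the uncontrolled test is significant. CR-LP has no controlled test of restriction at all. The SAP's reason for that exclusion, that two variables differ, applies with more force to the before-after test it leaves in place: there exercise, diet form and time are mixed in as well.

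**Conclusion.** The concern holds in limited form. A significant change from day 1 cannot be attributed to calorie restriction alone. That is weaker than saying the change is not a restriction effect, since restriction may well contribute. For CR-HP the defect is that the valid contrast depends on the wrong reference test. For CR-LP, a statement that restriction at normal protein suppressed or raised an outcome has only before-after support, although Hypothesis 2A calls for a comparison with CON on the formation markers. The CR-HP against CR-LP contrast is affected only through the conditional step.

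The rejection rates of 0.16 to 0.49 (n = 12, shifts of 0.2 to 0.5 SD) rest on an assumed n, alpha and shift. They should not be read as the plan's type I error: they are correct rejections of no change, and become errors only when the change is called a restriction effect. The design argument does not depend on these figures; it needs only that exercise and formula diet are common to all conditions, which the protocol states. The change is worth making, but the matter is one of interpretation and reporting, not a failure of the design.

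**What to change.** Amend section 4 along these lines:

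- The effect of restriction is the within-participant difference between the CR-HP change and the CON change. It is reported for every outcome with a 95% CI, whatever the result of any test against 0.
- The CR-LP minus CON difference in change is reported with a 95% CI where Hypothesis 2A needs it, labelled as the combined effect of energy and protein. The label meets the SAP's reason for leaving this comparison out.
- Claims about protein rest on the CR-HP minus CR-LP difference in change, also not conditional on a test against 0.
- Changes from day 1 within a condition are descriptive and are not evidence that restriction changed an outcome.

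The cost is SAP wording and a little extra analysis. The design already provides for all the data, and each participant is assigned to all three conditions. Some before-after results would lose the label of significance.
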